4.3. Type and Number of Subjects

In Part 1, up to 16 subjects with normal renal function will be matched to approximately 8 subjects with moderate renal impairment, and approximately 8 subjects with severe renal impairment and/or subjects with ESRD not on hemodialysis for a total of approximately 32 subjects. In Part 2 (optional), approximately 4 to 8 subjects with normal renal function (if enrolled), approximately 4 to 8 subjects with mild renal impairment, and approximately 4 to 8 subjects with ESRD on hemodialysis will be enrolled for a total of approximately 12 to 24 subjects.

If there are a sufficient number of subjects with normal renal function enrolled in Part 1 (Group A) that match subjects with renal impairment in other groups, a determination will be made regarding enrollment of matching subjects with normal renal function in Part 2 (Group D). In addition, if subjects prematurely discontinue the study, additional replacement subjects may be enrolled at the discretion of the Sponsor in consultation with the investigator.

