5.1. Inclusion Criteria

A subject will be eligible for inclusion in this study only if all of the following criteria apply:

AGE
1. Male or female subject between 18 and 80 years of age, inclusive.

TYPE OF SUBJECT AND DIAGNOSIS INCLUDING DISEASE SEVERITY
2. Healthy subject must be in clinically stable health as determined by the investigator based on medical history, clinical laboratory results (serum chemistry, hematology, urinalysis, and serology), vital sign measurements, 12-lead electrocardiogram (ECG) results, and physical examination findings. Subject with renal impairment must have clinical laboratory values consistent with their disease and are approved by the investigator.
3. Subject with renal impairment (mild, moderate, severe, or subjects with ESRD) may be taking medications, which in the opinion of the investigator, are believed to be therapeutic but do not affect study drug absorption, distribution, metabolism, or excretion. These medications must be stable doses taken for at least 7 days before the first dose of study drug. Any exceptions will be discussed with the sponsor or medical

monitor on a case-by-case basis and the reasons documented.

4. Subject with normal renal function or renal impairment (estimated eGFR corresponding to the calculated eGFR [the estimated eGFR may be rounded to the nearest integer]) at Screening (Section 6.2).
5. Subjects with ESRD on hemodialysis should be on hemodialysis for at least 3 months before Screening and is able to tolerate a hemodialysis treatment lasting 3 to 4 hours with blood flow rates of >200 mL/min.
6. Alanine aminotransferase (ALT) and bilirubin $1.5 \times$ upper limit of normal (ULN; isolated bilirubin >math>1.5 \times</math> ULN is acceptable, if bilirubin is fractionated and direct bilirubin <math><35\%</math>).

WEIGHT

7. Body weight ≥ 50 kg and BMI within the range 18.5 and 40 kg/m², inclusive.

SEX

8. Male or Female

A female subject is eligible to participate if she is not pregnant (as confirmed by a negative serum human chorionic gonadotrophin test), not lactating, and at least one of the following conditions applies:

- a Nonreproductive potential defined as:
 - Premenopausal females with one of the following:
 - Documented tubal ligation
 - Documented hysteroscopic tubal occlusion procedure with follow-up confirmation of bilateral tubal occlusion
 - Hysterectomy
 - Documented bilateral oophorectomy

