### 2.2. Study Objective(s) and Endpoint(s)

Objectives	Endpoints
Primary Objectives	Primary Endpoints

 
To compare the PK of gepotidacin administered as a 750 mg IV dose in normal healthy subjects compared with subjects with mild, moderate, and severe renal impairment, and with subjects with ESRD.
 
	
 
Plasma primary PK endpoints include AUC(0-∞) and Cmax of gepotidacin, as data permit
 
Urine primary PK end points include Ae total, AUC(t0-t1), fe%, and CLr of gepotidacin, as data permit
 
Dialysate primary PK end points include AUC(t0-t1), CLD, and Frem%(0-4), of gepotidacin, as data permit
 

Secondary Objectives	Secondary Endpoints

 
To assess the safety and tolerability of gepotidacin administered as a 750-mg IV dose in normal healthy subjects compared with subjects with mild, moderate, severe renal impairment, and with subjects with ESRD
 
	
 
12-lead safety electrocardiogram readings, change from baseline in vital sign measurements (blood pressure and heart rate), monitoring of adverse events, toxicity grading of clinical laboratory test results, and physical examinations
 

 
To evaluate the secondary PK parameters of gepotidacin administered as a 750-mg IV dose in normal healthy subjects compared with subjects with mild, moderate, and severe renal impairment, and with subjects with ESRD
 
	
 
Plasma PK endpoints include AUC(0-t), CL, λz, t1/2, Tmax, Vss, and Vz, as data permit
 
Urine PK endpoint includes Ae(t1-t2) and AUC(0-t) as data permit
 
Dialysate PK endpoints include Arem(0-1), Arem(1-2), Arem(2-3), Arem(3-4), and Arem(0-4), as data permit
 

Exploratory Objectives	Exploratory Endpoints

 
To evaluate the saliva pharmacokinetics of gepotidacin (subjects in Part 1 only).
 
	
 
Primary saliva PK endpoints include AUC(0-∞) and Cmax of gepotidacin, as data permit
 
Secondary saliva PK endpoints include AUC(0-t), CL, λz, t1/2, Tmax, Vss, Vz, RAUC(0-t) and RAUC(0-∞) as data permit
 

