Treatment Assignment	
 
Subjects will be enrolled into groups based on the classification as defined in the United States Food and Drug Administration draft guidance for industry, "Pharmacokinetics in Patients with Impaired Renal Function – Study Design, Data Analysis, and Impact on Dosing and Labeling" [DHHS, 2010]
 
Subjects with normal renal function and subjects with renal impairment will be classified based on the estimated glomerular filtration rate (eGFR; based on the Modification of Diet in Renal Disease Study). Subjects with normal renal function will also be classified based on estimated creatinine clearance (Clcr). 
 
Group A - normal renal function (eGFR <math>\geq 90</math> mL/min/1.73m^2)
 
Group B - moderate renal impairment (eGFR 30 to 59 mL/min/1.73m^2)
 
Group C - ESRD not on hemodialysis (eGFR <math>< 30</math> mL/min/1.73m^2)
 
Group D - normal renal function (eGFR <math>\geq 90</math> mL/min/1.73m^2)
 
Group E - mild renal impairment (eGFR 60 to 89 mL/min/1.73m^2)
 
Group F - ESRD on hemodialysis
 
 
 

Interim Analysis	
 
No formal interim analyses are planned for this study. However, all preliminary safety, tolerability, and available PK data will be reviewed internally at GSK after the approximate sample size has been reached in Part 1 and Part 2 (optional).
 
PK requirements must be met (observed mean values: AUC <math>< 48</math> <math>\mu\text{g}\cdot\text{hr}/\text{mL}</math> and Cmax <math>< 14</math> <math>\mu\text{g}/\text{mL}</math>) and safety and tolerability will be reviewed before enrolling subjects into Part 2 of the study
 

Overview of Study Design and Key Features	

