## 9.7. Appendix 7: Division of Microbiology and Infectious Disease Adult Toxicity Tables for Adverse Event Assessment

### 9.7.1. Laboratory Values

Parameter values are converted to use SI units.

HEMATOLOGY				
	Grade 1	Grade 2	Grade 3	Grade 4
Hemoglobin	95 to 105 G/L	80 to 94 G/L	65 to 79 G/L	<65 G/L
Absolute neutrophil count	1.0 to 1.5 $10^9/L$	0.75 to 0.999 $10^9/L$	0.5 to 0.749 $10^9/L$	<0.5 $10^9/L$
Platelets	75 to 99.999 $10^9/L$	50 to 74.999 $10^9/L$	20 to 49.999 $10^9/L$	<20 $10^9/L$
White Blood Cells	11 to 13 $10^9/L$	13 to 15 $10^9/L$	15 to 30 $10^9/L$	>30 or <1 $10^9/L$
% Polymorphonuclear leukocytes + band cells	>80%	90 to 95%	>95%	N/A
Abnormal Fibrinogen	Low: 1 to 2 G/L High: 4 to 6 G/L	Low: <1 G/L High: >6 G/L	Low: <0.5 G/L High: N/A	Fibrinogen associated with gross bleeding or with disseminated coagulation
Fibrin Split Product	0.020 to 0.040 G/L	0.041 to 0.050 G/L	0.051 to 0.060 G/L	>0.060 G/L
Prothrombin Time	1.01 to 1.25 $\times$ ULN	1.26 to 1.5 $\times$ ULN	1.51 to 3.0 $\times$ ULN	>3 $\times$ ULN
Activated Partial Thromboplastin	1.01 to 1.66 $\times$ ULN	1.67 to 2.33 $\times$ ULN	2.34 to 3 $\times$ ULN	>3 $\times$ ULN
Methemoglobin	5.0 to 9.9%	10.0 to 14.9%	15.0 to 19.9%	>20%

N/A = not applicable; ULN = upper limit of normal.

CHEMISTRIES				
	Grade 1	Grade 2	Grade 3	Grade 4
Hyponatremia	130 to 135 MMOL/L	123 to 129 MMOL/L	116 to 122 MMOL/L	<116 MMOL/L or abnormal sodium with mental status changes or seizures
Hypernatremia	146 to 150 MMOL/L	151 to 157 MMOL/L	158 to 165 MMOL/L	>165 MMOL/L or abnormal sodium with mental status changes or seizures
Hypokalemia	3.0 to 3.4 MMOL/L	2.5 to 2.9 MMOL/L	2.0 to 2.4 MMOL/L or intensive replacement therapy of hospitalization required	<2.0 MMOL/L or abnormal potassium with paresis, ileus, or life-threatening arrhythmia
Hyperkalemia	5.6 to 6.0 MMOL/L	6.1 to 6.5 MMOL/L	6.6 to 7.0 MMOL/L	>7.0 MMOL/L or abnormal potassium with life-threatening arrhythmia
Hypoglycemia	3.0 to 3.55 MMOL/L	2.22 to 2.99 MMOL/L	1.67 to 2.21 MMOL/L	<1.67 MMOL/L or abnormal glucose with mental status changes or coma
Hyperglycemia (nonfasting and no prior diabetes)	6.44 to 8.88 MMOL/L	8.89 to 13.88 MMOL/L	13.89 to 27.75 MMOL/L	>27.76 MMOL/L or abnormal glucose with ketoacidosis or seizures
Hypocalcemia (corrected for albumin)	2.10 to 1.95 MMOL/L	1.94 to 1.75 MMOL/L	1.74 to 1.52 MMOL/L	<1.52 MMOL/L or abnormal calcium with life-threatening arrhythmia or tetany

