Hypercalcemia (corrected for albumin)	2.64 to 2.87 MMOL/L	2.88 to 3.12	3.13 to 3.37 MMOL/L	>3.37 MMOL/L or abnormal calcium with life-threatening arrhythmia
Hypomagnesemia	0.7 to 0.6 MMOL/L	0.59 to 0.45 MMOL/L	0.44 to 0.3 MMOL/L	<0.3 MMOL/L or abnormal magnesium with life-threatening arrhythmia
Hypophosphatemia	0.7 to 0.8 MMOL/L	0.5 to 0.6 MMOL/L or replacement Rx required	0.3 to 0.4 MMOL/L intensive therapy or hospitalization required	<0.3 MMOL/L or abnormal phosphate with life-threatening arrhythmia
Hyperbilirubinemia (when accompanied by any increase in other liver function test)	1.1 to <1.25 × ULN	1.25 to <1.5 × ULN	1.5 to 1.75 × ULN	>1.75 × ULN
Hyperbilirubinemia (when other liver function tests are in the normal range)	1.1 to <1.5 × ULN	1.5 to <2.0 × ULN	2.0 to 3.0 × ULN	>3.0 × ULN
Blood urea nitrogen	1.25 to 2.5 × ULN	2.6 to 5 × ULN	5.1 to 10 × ULN	>10 × ULN
Hyperuricemia (uric acid)	446 to 595 UMOL/L	596 to 714 UMOL/L	715 to 892 UMOL/L	>892 UMOL/L
Creatinine	1.1 to 1.5 × ULN	1.6 to 3.0 × ULN	3.1 to 6.0 × ULN	>6 × ULN or dialysis required

Rx = therapy; ULN = upper limit of normal.

ENZYMES				
	Grade 1	Grade 2	Grade 3	Grade 4
Aspartate aminotransferase	1.1 to <2.0 × ULN	2.0 to <3.0 × ULN	3.0 to 8.0 × ULN	>8.0 × ULN
Alanine aminotransferase	1.1 to <2.0 × ULN	2.0 to <3.0 × ULN	3.0 to 8.0 × ULN	>8.0 × ULN
Gamma to glutamyl transferase	1.1 to <2.0 × ULN	2.0 to <3.0 × ULN	3.0 to 8.0 × ULN	>8.0 × ULN
Alkaline Phosphatase	1.1 to <2.0 × ULN	2.0 to <3.0 × ULN	3.0 to 8.0 × ULN	>8.0 × ULN
Amylase	1.1 to 1.5 × ULN	1.6 to 2.0 × ULN	2.1 to 5.0 × ULN	>5.1 × ULN
Lipase	1.1 to 1.5 × ULN	1.6 to 2.0 × ULN	2.1 to 5.0 × ULN	>5.1 × ULN

ULN = upper limit of normal.

URINALYSIS				
	Grade 1	Grade 2	Grade 3	Grade 4
Proteinuria	1+ or 200 MG to 1 GM loss/day	2 to 3+ or 1 to 2 GM loss/day	4+ or 2 to 3.5 GM loss/day	Nephrotic syndrome or >3.5 GM loss/day
Hematuria	Microscopic only <10 RBC/HPF	Gross, no clots >10 RBC/HPF	Gross, with or without clots, or red blood cells casts	Obstructive or required transfusion

HPF = high-powered field; RBC = red blood cells.

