## 9.11.8. ICH Listings

ICH : Listings					
No.	Population	IDSL / TST ID / Example Shell	Title	Programming Notes	Deliverable [Priority]
Randomisation					
1	Safety	SAFE_L1	Listing of Renal Function and Group		SAC [1]
Subject Disposition					
2	Safety	ES2	Listing of Reasons for Study Withdrawal		SAC [1]
3	Screened	ES7	Listing of Reasons for Screening Failure		SAC [1]
4	Screened	DV2	Listing of Important Protocol Deviations		SAC [1]
5	Safety	IE3	Listing of Subjects with Inclusion/Exclusion Criteria Deviations		SAC [1]
Demographics					
6	Safety	DM2	Listing of Demographic Characteristics	Include height, weight and BMI	SAC [1]
7	Safety	DM9	Listing of Race		SAC [1]
Medical Conditions and Concomitant Medications					
8	Safety	MH2	Listing of Medical Conditions		SAC [1]
9	Safety	CM3	Listing of Concomitant Medications		SAC [1]
Exposure					
10	Safety	SAFE_L1	Listing of Exposure Data		SAC [1]
Safety					
11	Safety	AE2	Listing of Relationship Between System Organ Class and Verbatim Text		SAC[1]
12	Safety	AE7	Listing of Subject Numbers for Individual Adverse Events		SAC [1]
13	Safety	AE8	Listing of All Adverse Events		SAC [1]

ICH : Listings					
No.	Population	IDSL / TST ID / Example Shell	Title	Programming Notes	Deliverable [Priority]
14	Safety	AE8	Listing of Study Drug Related Adverse Events		SAC [1]
15	Safety	SAFE_L2	Listing of Serious Adverse Events		SAC [1]
16	Safety	AE8	Listing of Adverse Events Leading to Withdrawal from Study		SAC [1]
17	Safety	SAFE_L3	Listing of Infusion Site Reaction Adverse Events	Conditional display	SAC [1]
18	Safety	SAFE_L4	Listing of Liver Adverse Events	Conditional display	SAC [1]
19	Safety	SAFE_L5	Listing of Cardiovascular Adverse Events	Conditional display	SAC [1]
20	Safety	SAFE_L6	Listing of Allergic Reaction Adverse Events	Conditional display	SAC [1]
21	Safety	SAFE_L7	Listing of Clostridium Difficile Testing	Conditional display	SAC [1]
22	Safety	SAFE_L8	Listing of Rash Events	Conditional display	SAC [1]
Laboratory Measurements					
23	Safety	LB5	Listing of Clinical Chemistry Toxicities of Grade 3 or Higher		SAC [1]
24	Safety	LB5	Listing of All Clinical Chemistry Data for Subjects with Toxicities of Grade 3 or Higher		SAC [1]
25	Safety	LB5	Listing of Haematology Toxicities of Grade 3 or Higher		SAC [1]
26	Safety	LB5	Listing of All Haematology Data for Subjects with Toxicities of Grade 3 or Higher		SAC [1]

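### Laboratory toxicity grades are not related to the pre-dose grade, so creatinine grades in Group F, and in part of Group C, would describe the kidney disease rather than the drug

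*SAP*

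**What the plan says.** SAP 2.2 lists "toxicity grading of clinical laboratory test results, and physical examinations" among the secondary safety endpoints, under an objective that compares normal subjects with each renal impairment group and with ESRD.

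SAP 9.7.1 gives the grading tables. The only data step it describes is that "Parameter values are converted to use SI units". Creatinine is Grade 3 from 3.1 to 6.0 × ULN and Grade 4 above 6 × ULN "or dialysis required". Protocol Appendix 6 has the same criterion.

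The group definition in SAP 2.3 reads "Group F - ESRD on hemodialysis". Protocol 5.1 adds: "Subjects with ESRD on hemodialysis should be on hemodialysis for at least 3 months before Screening". On size, Protocol 4.3 says that "approximately 4 to 8 subjects with ESRD on hemodialysis will be enrolled" in optional Part 2.

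Grades reach the report through Listings 23 to 28 in SAP 9.11.8, of which the first is "Listing of Clinical Chemistry Toxicities of Grade 3 or Higher". None of the six titles or programming notes refers to baseline, worsening or emergence after dosing. The safety tables in SAP 9.11.5 contain no summary of laboratory grades. SAP 9.3.2.1 defines baseline as the last value before dosing in each period, but uses it for change from baseline and not for grading.

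**The concern.** A toxicity grade informs about a drug when it is new or higher after dosing. Here the groups are defined by renal function, and creatinine is one of the graded analytes. With absolute grades, the groups differ on creatinine grade before anyone is dosed. Where a subject starts at the top grade, no worsening of that grade can be recorded.

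At stake is whether one component of a secondary safety endpoint can be read as intended. No PK estimate is involved, and Protocol 9.4.2.1 rules out inferential testing of safety variables.

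**Working it through.** The plan states no figure to reproduce. The check has three parts.

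**1. Group F, by definition.** Grade 4 creatinine needs either more than 6 × ULN or a need for dialysis. Every Group F subject is on hemodialysis, for at least 3 months before Screening. The second condition is therefore met whatever the creatinine value: 4 of 4 up to 8 of 8 subjects are Grade 4 before dosing. Grade 4 is the highest grade, so no increase is possible. Listing 24, which prints all chemistry for anyone with a Grade 3 or higher value, would include every Group F subject, so the filter selects nobody within that group.

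**2. Other groups, by arithmetic.** Protocol 6.2 gives the MDRD equation, reading −1.154 and −0.203 as exponents. Solved for serum creatinine (mg/dL):

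Scr = [175 × age^(−0.203) × factors ÷ eGFR]^(1/1.154)

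The factors are 0.742 if female and 1.212 if African American. Example, man aged 60, factors 1, eGFR 15: 175 × 60^(−0.203) ≈ 76.2; 76.2 ÷ 15 ≈ 5.08; 5.08^(1/1.154) ≈ 4.09 mg/dL.

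The ULN is an assumption, because the documents give none: 1.2 to 1.4 mg/dL for men and 1.0 to 1.2 for women. The example then gives 4.09 ÷ 1.4 = 2.92 to 4.09 ÷ 1.2 = 3.41 × ULN, which is Grade 2 or 3. The table leaves a gap between 3.0 and 3.1 × ULN; values of 3.05 or more are taken as Grade 3.

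Range over both sexes and ages 40 to 75, without the 1.212 factor:

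| eGFR | Creatinine, × ULN | Grade at entry |
|---|---|---|
| 29 | 1.43 to 2.07 | 1 to 2 |
| 20 | 1.97 to 2.85 | 2 |
| 15 | 2.53 to 3.66 | 2 to 3 |
| 10 | 3.60 to 5.20 | 3 |
| 5 | 6.56 to 9.48 | 4 |

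With the 1.212 factor, Grade 3 can begin nearer eGFR 20: a man aged 40 has 4.04 mg/dL, which is 2.89 to 3.37 × ULN. At eGFR 60 or above (Groups A, D and E) the grade is at most 1, and in Group B at most 2. Group C takes eGFR below 30 and includes ESRD not on hemodialysis, so some of its subjects could enter at Grade 3, and at the very lowest eGFR at Grade 4.

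**3. Timing in Group F.** Per Protocol 4.2 and Table 4, Period 1 laboratory samples are on Day −1 and Day 2, with dialysis after the start of dosing on Day 1. Period 2 samples are on Day 7 and Day 9, with dialysis before dosing on Day 8. A dialysis session lies between the pre-dose and post-dose samples in both periods, so a change in creatinine or BUN is mixed with removal by dialysis.

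**The case against.** The strongest reply is that little is lost, and several of its parts stand.

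- A reader might infer that the Grade 3 or higher displays cannot show a drug effect. The documents do not support that. The dialysis clause sits in the creatinine row only. Potassium, sodium, ALT, AST, bilirubin and hematology have none, so a new Grade 3 value in these would still be listed in any group.
- Worsening is not hidden altogether. Table 2.3 summarises chemistry change from baseline, and Listing 24 prints the full chemistry of flagged subjects. Both stand as mitigation, but neither shows a change in grade, and grading is the named endpoint.
- A reader might infer that many Group C subjects enter at Grade 3. That depends on a ULN the documents do not give and on who enrols, and Protocol 9.4.1 itself foresees eGFR clustering at the higher end of the range. BUN has no dialysis clause and needs more than 5 × ULN for Grade 3.
- The SAP does not say that the non-numeric clause will be programmed, so Grade 4 for all of Group F is the literal reading and not a certain output. Without the clause, the grade turns on whether creatinine exceeds 6 × ULN. Two programmers could produce different listings from the same data, which is a reason to state the rule.
- A reader might infer that numeric grading alone makes Group F creatinine interpretable. It does not, because of the dialysis session between samples.
- Protocol Appendix 5 keeps disease-related laboratory findings out of adverse events unless they exceed what the subject's condition explains. That governs event reporting, not laboratory grading. Appendix 6 allows protocol-specific criteria to override its tables, but neither document supplies one here.

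**Conclusion.** The point holds for creatinine grades and for the absence of any graded display relative to baseline. Under the literal rule, all 4 to 8 Group F subjects are creatinine Grade 4 before dosing. Some Group C subjects may enter at Grade 3, from an eGFR of about 15 downwards under assumed ULNs of 1.0 to 1.4 mg/dL. In these subjects the creatinine grade reflects renal disease.

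The consequence is minor. Group F is optional, the outputs are descriptive listings for a secondary endpoint, and other analytes and the ungraded displays still inform. The change is worth making because the plan has no other display of change in laboratory grade and the data are already scheduled.

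**What to change.** 1. Add a table by group of the shift from the latest pre-dose grade in the period (Day −1; Day 7 for Group F Period 2) to the worst post-dose grade.
2. In Listings 23 to 28, flag post-dose values whose grade exceeds that pre-dose grade. Keep every Grade 3 or higher value listed; restricting the listings to new events would remove safety data from view.
3. State in SAP 9.7.1 that the dialysis clause is not applied in the laboratory grading of subjects already on dialysis at entry, so that their creatinine is graded on multiples of ULN.
4. Footnote that Group F creatinine and BUN shifts span a dialysis session and are not interpretable as drug effect.

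The cost is one extra table and a flag, with no new samples, visits or subjects.

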**9.8. Appendix 8: Multiple Comparisons & Multiplicity**

**9.8.1. Handling of Multiple Comparisons & Multiplicity**

No adjustments for multiplicity will be made.

**9.9. Appendix 9: Model Checking and Diagnostics for Statistical Analyses****9.9.1. Statistical Analysis Assumptions**

Endpoint(s)	

• PK endpoints include AUC(0-∞), AUC(0-t) and Cmax

Analysis	

• Analysis of variance

• Linear regression

• Model assumptions will be applied, but appropriate adjustments may be made based on the data.

	

## 9.10. Appendix 10 – Abbreviations & Trade Marks

### 9.10.1. Abbreviations

Abbreviation	Description
ADaM	Analysis Data Model
AE	Adverse Event
Ae(t1-t2)	Amount of drug excreted in urine in a time intervals
Ae total	Total unchanged drug (total amount of drug excreted in urine)
A&R	Analysis and Reporting
Arem(0-1)	Amount of drug removed by hemodialysis from time 0 to 1 hour after the start of hemodialysis
Arem(1-2)	Amount of drug removed by hemodialysis from time 1 to 2 hours after the start of hemodialysis
Arem(2-3)	Amount of drug removed by hemodialysis from time 2 to 3 hours after the start of hemodialysis
Arem(3-4)	Amount of drug removed by hemodialysis from time 3 to 4 hours after the start of hemodialysis
Arem(0-4)	Cumulative amount of drug removed by hemodialysis from time 0 to 4 hours after the start of hemodialysis
AUC(0-∞)	Area under the concentration-time curve from time 0 (predose) extrapolated to infinite time
AUC(0-t)	Area under the concentration-time curve from time 0 (predose) to time of last quantifiable concentration
AUC(0-t)	Area under the urine concentration-time curve from time 0 to the corresponding urine collection interval.
AUC(t0-t1)	Partial area under the curve estimated from predialyzer samples collected from start of dialysis (t0) to end of dialysis (t1)
AUC(0-12)	Partial area under the curve estimated from urine concentrations samples collected from predose to 12 hours post dose
AUC(0-24)	Partial area under the curve estimated from urine concentrations samples collected from predose to 24 hours post dose
AUC(0-48)	Partial area under the curve estimated from urine concentrations samples collected from predose to 48 hours post dose
CDISC	Clinical Data Interchange Standards Consortium
CI	Confidence Interval
CL	Systemic clearance
CLD	Dialysis clearance
CL r	Renal clearance of drug
C max	Maximum observed concentration
CS	Clinical Statistics
CSR	Clinical Study Report
CTR	Clinical Trial Register
CV b / CV w	Coefficient of Variation (Between) / Coefficient of Variation (Within)
DOB	Date of Birth

Abbreviation	Description
DP	Decimal Places
Frem%(0-4)	Fraction (%) of the dose removed by hemodialysis from 0 to 4 hours after the start of hemodialysis (or to the end of dialysis if less than 4 hours)
fe%	Percentage of the given dose of drug excreted in urine
GUI	Guidance
GSK	GlaxoSmithKline
eCRF	Electronic Case Record Form
IA	Interim Analysis
ICH	International Conference on Harmonisation
IDSL	Integrated Data Standards Library
IP	Investigational Product
GUI	Guidance
PCI	Potential Clinical Importance
PK	Pharmacokinetic
QC	Quality Control
QTcF	Frederica's QT Interval Corrected for Heart Rate
QTcB	Bazett's QT Interval Corrected for Heart Rate
RAP	Reporting & Analysis Plan
RAUC(0-t)	The ratio of the AUC(0-t) observed in saliva relative to the AUC(0-t) in plasma
RAUC(0-∞)	The ratio of the AUC(0-∞) observed in saliva relative to the AUC(0-∞) in plasma
SAC	Statistical Analysis Complete
SDTM	Study Data Tabulation Model
SOP	Standard Operation Procedure
t 1/2	Terminal phase half life
λ z	Terminal-phase rate constant
TA	Therapeutic Area
TFL	Tables, Figures & Listings
T max	Time to first occurrence of C max
V ss	Volume of distribution at steady-state of parent drug
V z	Volume of distribution of the terminal phase
GSK	GlaxoSmithKline

